3.2 Secondary Objectives

The secondary objectives for this study are:

- To characterize dose-limiting toxicities (DLTs), maximum tolerated dose (MTD), and recommended phase 2 dose (RP2D) for the combination.
- To assess other measures of anti-tumor activity of the combination of pembrolizumab and cabozantinib in subjects with locally advanced or metastatic renal cell carcinoma.
 - irRECIST (Immune-related response criteria) response
 - Progression-free survival
 - Overall survival
 - Time to progression of overall disease
 - Time to progression of bone metastasis or skeletal-related event
 - Clinical benefit rate [complete response (CR) + partial response (PR) + stable disease (SD)]
 - Duration of response or disease stability
 - Duration on treatment in subjects treated beyond progression

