4.0 BACKGROUND & RATIONALE

4.1 Background

Over the past decade, multiple vascular endothelial growth factor (VEGF) and molecular target of rapamycin (mTOR) pathway targeted therapies have been approved and have significantly improved the morbidity and mortality among subjects with advanced or metastatic renal cell carcinoma (mRCC). Nevertheless, mRCC remains a largely incurable disease. Tyrosine kinase inhibitors (TKI) and VEGF-directed antibodies are widely used as standard first- and second-line treatments for metastatic RCC. Despite the improvements seen with the currently available VEGF-directed therapies, treatment resistance and disease progression occur in the majority of subjects with continued treatment and these agents do not produce durable responses.[1] Acquired resistance to vascular endothelial growth factor (VEGF) pathway inhibitors is frequently mediated through the activation of alternative signaling pathways that restore tumor perfusion, including upregulation of the expression of angiopoietins, c-MET, activin receptor-like kinase-1 (ALK-1) receptor and interleukin 8 (IL-8), and loss of p53 function.[2] In addition, VEGF also acts as an immunosuppressive molecule and can inhibit maturation of dendritic cells, promote immune suppressive cell infiltration and enhance immune checkpoint molecules expression.[3]

Renal cell carcinoma is an immunogenic tumor with a dysfunction immune cell infiltrate that allows malignant progression through evasion of immune surveillance. Novel immunemodulating agents that target cytotoxic T-lymphocyte-associated antigen 4 (CTLA-4) and programmed death receptor-1 (PD-1) significantly enhances antitumor immunity.[4] The benefit of anti-PD-1 antibodies in the treatment of mRCC was confirmed in the CheckMate 025 study, which was a phase III study of nivolumab (an anti-PD-1 antibody) vs. everolimus in the second-line treatment of mRCC. Compared to everolimus, nivolumab showed significant improvements in overall survival (25.0 vs. 19.6 months; HR 0.73; P=0.002) and objective response rate (25% vs. 5%).[5]

Recent major discoveries in tumor immunology and agents that can trigger immune responses, along with better understanding of the mechanisms of VEGF inhibitor therapy provide rationale for combination therapies in the treatment of mRCC. There are multiple proposed mechanisms of synergy between inhibiting both VEGF- and PD-1. In addition to angiogenic

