7.1.5.4 Survival Follow-Up

Patients will be followed for survival every 6 months (± 1 month) for 3 years after completion of study treatment or until study discontinuation, whichever occurs first.

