8.2.3 Analysis of Anti-Tumor Activity

Descriptive statistics will be used to summarize all demographic and analytic data. Continuous data will be summarized using means, standard deviation, range, etc. Categorical data will be summarized using frequency tables.

Tumor response analyses will be based on definitions of responses according to both RECIST v1.1 and immune-related response criteria (irRECIST).

Objective response is defined as a complete or partial response, as determined by investigator assessment using RECIST and irRECIST. Subjects with missing or no response assessments will be classified as non-responders. For the primary objective, a one-sided exact binomial test will be used to assess whether the ORR is significantly greater than 20% in subjects taking a combination of pembrolizumab and cabozantinib.

Clinical benefit rate (CR + PR +SD) and duration will also be recorded.

Among subjects with an objective response, duration of response will be defined as the time from first occurrence of a documented objective response until the time of documented disease progression or death from any cause during the study, whichever occurs first. For all other subjects, duration of objective response will be censored at the day of the last tumor assessment.

Progression-free survival (PFS) will be defined as the time from study treatment initiation (Cycle 1, Day 1) to the first occurrence of documented disease progression or death from any cause during the study, whichever occurs first. For subjects who do not have documented progressive disease or death during the study, PFS will be censored at the day of the last tumor assessment.

Overall survival (OS) will be defined as the time from study treatment initiation (Cycle 1, Day 1) to death from any cause. For subjects who do not have documented death during or after the study, OS will be censored at the day of known survival status.

In subjects with bone metastases, time to progression of bone metastases or skeletal related event (SRE, defined as pathologic fracture, spinal cord compression, and radiation to bone or surgery to bone related to cancer) will also be recorded from Cycle 1 Day 1 to the time of progression or SRE.

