Progression-free survival, overall survival, duration of response/duration on treatment, and time to skeletal related event or bone progression will be assessed using Kaplan-Meier curves and hazard ratios. The clinical benefit rate and duration of clinical benefit will be summarized using descriptive statistics.

Among subjects who receive treatment beyond progression, duration on treatment will be recorded.

Response data may be listed, summarized in tables, and/or presented as a swimmer plot.

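### Time to bone progression or skeletal event is planned as a Kaplan-Meier analysis with no rule for death; read as risk, one minus that curve is too high

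*Combined protocol and SAP*

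**What the plan says.** Section 3.2 lists "Time to progression of bone metastasis or skeletal-related event" among the secondary objectives, and Section 4.2.1 gives it a rationale of its own. Section 8.2.3 restricts the endpoint to subjects with bone metastases and says that it "will also be recorded from Cycle 1 Day 1 to the time of progression or SRE". The skeletal component is given as "SRE, defined as pathologic fracture, spinal cord compression, and radiation to bone or surgery to bone related to cancer". Death appears in neither part. The same section then states that "time to skeletal related event or bone progression will be assessed using Kaplan-Meier curves and hazard ratios".

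The neighbouring endpoints are specified more fully. The PFS event is the "first occurrence of documented disease progression or death from any cause during the study, whichever occurs first", and for subjects with neither, "PFS will be censored at the day of the last tumor assessment". Duration of response also counts death and has a censoring rule, and overall survival has a censoring rule. The bone endpoint has no censoring rule. The documents nowhere mention competing risks, cumulative incidence or a composite of bone event and death.

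Two follow-up provisions bear on this. Under Section 5.6.3, disease status after treatment is followed only in subjects who stopped for a reason other than progression, and at the latest until progression. Under Section 7.1.5.4, survival is followed every 6 months "for 3 years after completion of study treatment or until study discontinuation, whichever occurs first".

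**The concern.** A subject who dies without a bone event can never have one. Kaplan-Meier has only two categories, event and censored, so a death that is not an event has to be censored. The subject then leaves the risk set, and the method assumes that the subject's later bone-event risk would have matched that of the subjects still followed. One minus the resulting curve estimates the bone-event probability in a hypothetical setting without death, and that exceeds the proportion of subjects who actually have a bone event. A larger sample does not remove the difference.

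Section 5.2.3 describes a single-arm trial. The absolute curve is therefore what readers will use, with no control arm carrying the same distortion. If the complement of the curve is reported as bone-event risk, control of bone disease will look worse than it was, on an outcome that Section 4.2.1 presents as an unmet need.

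**Working it through.** The plan gives no figure for this endpoint, so there is nothing to reproduce. What follows is an illustration under stated assumptions.

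**Inputs**
- Event definition and method: Section 8.2.3, as above.
- Median time to bone event: not in the documents. Assumed 6, 12 or 24 months.
- Median time to death without a prior bone event: not in the documents. Assumed 19.6, 25, 40 or 60 months. The two shorter values are the median overall survival figures that Section 4.1 cites from the second-line trial of nivolumab against everolimus. They are all-cause figures and include any deaths after a bone event, so they may overstate the competing hazard. The two longer values allow for that.
- Hazards constant and independent; bone status followed until bone event or death.

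**Formulas**, with λb = ln 2 / (bone-event median) and λd = ln 2 / (death median):
- One minus Kaplan-Meier, deaths censored: 1 − exp(−λb·t)
- Cumulative incidence: [λb / (λb + λd)] · [1 − exp(−(λb + λd)·t)]

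**One case worked through**, medians 12 and 25 months: λb = 0.0578, λd = 0.0277, λb / (λb + λd) = 25/37 = 0.676.
- 12 months: 1 − exp(−0.693) = 0.500, against 0.676 × (1 − exp(−1.026)) = 0.433. Difference 0.067.
- 24 months: 1 − exp(−1.386) = 0.750, against 0.676 × (1 − exp(−2.052)) = 0.589. Difference 0.161.

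A simulation of this case with 12 subjects (an assumed subgroup size) gave means of 0.746 and 0.589 at 24 months, in agreement.

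**Whole grid**, one minus Kaplan-Meier less cumulative incidence, at 12 months / 24 months:

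| Bone-event median | Death 19.6 | Death 25 | Death 40 | Death 60 |
|---|---|---|---|---|
| 6 | 0.110 / 0.192 | 0.088 / 0.157 | 0.057 / 0.104 | 0.039 / 0.071 |
| 12 | 0.083 / 0.196 | 0.067 / 0.161 | 0.043 / 0.108 | 0.029 / 0.075 |
| 24 | 0.051 / 0.147 | 0.041 / 0.121 | 0.027 / 0.081 | 0.018 / 0.056 |

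The difference is positive in every cell: 0.018 to 0.110 at 12 months and 0.056 to 0.196 at 24 months.

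**Six months.** With medians 12 and 24 months the two quantities are 0.293 and 0.270. With medians 18 and 25 months they are 0.206 and 0.191. The difference is about 0.02 in both.

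**Against sampling error.** If 12 to 20 subjects have bone metastases (assumed), the standard error of a proportion of 0.43 runs from √(0.43 × 0.57 / 12) = 0.14 to √(0.43 × 0.57 / 20) = 0.11. The 12-month difference of 0.067 in the worked case is roughly half of that.

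**The case against.** The strongest reply has four parts.

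First, the plan does not say that deaths are censored. A reader might infer that the SAP prescribes it. It does not: censoring follows from the event definition combined with Kaplan-Meier, and the documented defect is a missing rule. The inference is firm, because the method leaves no other place for a death that is not an event, but it remains an inference.

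Second, the plan calls for curves and hazard ratios. It does not commit to reporting one minus the curve as a probability. Censoring deaths is an accepted way to estimate a cause-specific hazard. A reader might conclude that the planned estimate will in any case make bone control look worse; the documents support that only if the curve is read as absolute risk. In a single-arm trial that is the natural reading, and Section 8.2.3 names no comparison for the hazard ratios, so the concern stands in conditional form.

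Third, the size is modest where data will be available. Section 1.0 expects about 8 months of treatment on average, and Section 6.0 schedules scans during treatment cycles, not at survival follow-up. Bone status at 24 months will probably be known for few subjects, so the 6- and 12-month differences matter more than the larger later ones. This stands.

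Fourth, death may not be the main threat. Because disease follow-up stops at progression under Section 5.6.3, a subject who progresses outside bone may lose bone assessment well before death, unless treated beyond progression under Section 5.7. If most deaths come after that point, few will be observed while bone status is still assessed. Aalen-Johansen and Kaplan-Meier will then differ less, and neither deals with the informative loss of follow-up. This also stands. It would be wrong to infer that naming death as a competing event repairs the endpoint completely.

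**Conclusion.** The concern holds in a limited form. As written, the bone endpoint excludes death and is assigned to Kaplan-Meier. Deaths without a prior bone event would by implication be censored, and one minus the curve, if read as the risk of a bone event, is too high. The direction does not depend on the assumed rates; the size does. The figures above rest on constant, independent hazards and on bone status being followed to bone event or death, neither of which the documents establish. The size given here should be treated as a range and not as a prediction.

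The consequence is confined to a descriptive secondary endpoint in the bone-metastasis subgroup. It has no hypothesis test or decision rule. The documents give no ground for extending the point to the primary response-rate test, which does not use this analysis, or to PFS and overall survival, where death is an event.

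**What to change.** In Section 8.2.3, replace Kaplan-Meier for this endpoint and add a censoring rule:

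- Estimate the cumulative incidence of bone progression or skeletal-related event by the Aalen-Johansen method, with death without a prior bone event as a competing event. Report 6- and 12-month values with 95% confidence intervals.
- Censor subjects whose bone assessment ends, for example at non-bone progression, at their last bone assessment. State that deaths after bone follow-up has ended are not counted as competing events, and define when bone follow-up ends.
- Report the number of subjects censored in this way, and name the censoring as a limitation because it may be informative.
- Keep Kaplan-Meier for PFS and overall survival.

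The cost is a short paragraph in the SAP and a standard software routine. Survival status is already collected under Sections 6.0 and 7.1.5.4, so the competing event needs no new data. The change will not make the estimates precise in a small subgroup, and it does not recover bone status after assessment has stopped.

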8.0 STATISTICAL ANALYSIS PLAN

8.1 Statistical Analysis Plan Summary

The final study analysis will be based on subject data collected through study discontinuation. Analyses will be based on the safety-evaluable population, defined as all subjects who receive any amount of study treatment. In general, data will be summarized as warranted, and listings will be provided in place of tables when sample sizes are small. Summaries will be presented by the assigned dose regimen and designated treatment arm.

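### Duration of clinical benefit is a censored time, but Section 8.2.3 assigns it to descriptive statistics and gives it no start, end or censoring rule

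*Combined protocol and SAP*

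**What the plan says.** Section 3.2 lists "Duration of response or disease stability" among the secondary objectives.

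Section 8.2.3 first introduces the variable with "Clinical benefit rate (CR + PR +SD) and duration will also be recorded", and gives no start, end or censoring rule. Later in the section PFS and OS, together with "duration of response/duration on treatment, and time to skeletal related event or bone progression will be assessed using Kaplan-Meier curves and hazard ratios", are given a time-to-event method. The next sentence separates this duration from that group: "The clinical benefit rate and duration of clinical benefit will be summarized using descriptive statistics". For continuous data in general, the same section says: "Continuous data will be summarized using means, standard deviation, range, etc".

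The neighbouring endpoints do have censoring rules. For subjects without progression or death, "PFS will be censored at the day of the last tumor assessment". For duration of response the rule is: "For all other subjects, duration of objective response will be censored at the day of the last tumor assessment".

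Section 8.1 sets the data cut: "The final study analysis will be based on subject data collected through study discontinuation". Section 5.6.3 adds that disease follow-up in subjects who stop treatment without progression can end with a new cancer treatment, withdrawal of consent or loss to follow-up.

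**The concern.** Clinical benefit ends at progression or death, the same events that end PFS and duration of response. The plan treats those two as censored when the event has not been seen. Duration of clinical benefit is incomplete in the same subjects for the same reasons, yet it is the one assigned to a method with no provision for incomplete times.

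It is also the only analysis in Section 8.2.3 that covers the disease-stability half of the secondary objective. A raw mean for it would be printed beside a Kaplan-Meier duration of response, and the two could not be compared. Subjects with the longest benefit are the most likely to be incomplete, so the error runs towards a shorter reported duration.

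**Working it through.** **Plan's own figures.** No figure in the plan depends on this duration. The efficacy design figures in Section 8.2.5 reproduce under that section's rule (stop at 2 or fewer of 20; effective above 12 of 38; 0.20 against 0.50): type I error 0.029, type II error 0.017, early termination 0.206, expected size 20 + (1 − 0.206) × 18 = 34.29. None of them uses duration of clinical benefit.

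**Inputs from the documents**
- Enrollment 3 years and trial duration 5 years (Section 1.0). With uniform accrual, potential follow-up C is uniform from 60 − 36 = 24 to 60 months.
- Median PFS of 7.4 months (cabozantinib phase III, Section 4.1.1.2) and 12.9 months (cabozantinib phase 1 in RCC, Section 4.2.2.2), used as illustrative medians.

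**Assumptions not in the documents**
- Exponential durations, uniform accrual and non-informative censoring.
- A share d who would leave before progression, taken as 0, 10% or 30%.

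**Formula.** Let λ = ln 2 / median, so the true mean is 1/λ. With early leaving at a constant rate, κ = λ/(1 − d). Define q(κ) = (e^(−24κ) − e^(−60κ)) / (36κ). The mean of observed times is (1/κ)(1 − q(κ)). Its ratio to the true mean is (1 − d)(1 − q(κ)).

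**Administrative censoring only (d = 0)**
- Median 7.4: λ = 0.09367, true mean 10.68. q = (0.1056 − 0.0036)/3.372 = 0.0302. Mean of observed times 10.35, about 3% low.
- Median 12.9: λ = 0.05373, true mean 18.61. q = (0.2754 − 0.0398)/1.934 = 0.1218. Mean of observed times 16.34, about 12% low.

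**A further 30% leaving (d = 0.3)**
- Median 7.4: κ = 0.1338, q = 0.0083, ratio 0.7 × 0.9917 = 0.694, about 31% low.
- Median 12.9: κ = 0.0768, q = 0.0537, ratio 0.7 × 0.9463 = 0.662, about 34% low.

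**Both ways of handling ongoing subjects.** A simulation of 2,000,000 durations per scenario agrees with the formula and adds the mean when ongoing subjects are left out (months):

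| True median | True mean | d | Mean, ongoing counted at observed time | Mean, ongoing left out | Median of observed times |
|---|---|---|---|---|---|
| 7.4 | 10.7 | 0 | 10.3 (−3%) | 9.6 (−10%) | 7.4 |
| 7.4 | 10.7 | 10% | 9.4 (−12%) | 8.9 (−17%) | 6.7 |
| 7.4 | 10.7 | 30% | 7.4 (−31%) | 7.2 (−32%) | 5.2 |
| 12.9 | 18.6 | 0 | 16.3 (−12%) | 13.5 (−27%) | 12.9 |
| 12.9 | 18.6 | 10% | 15.1 (−19%) | 12.8 (−31%) | 11.6 |
| 12.9 | 18.6 | 30% | 12.3 (−34%) | 11.1 (−41%) | 9.0 |

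The Kaplan-Meier median returned 7.4 and 12.9 in every row. With d = 0 the median of observed times is also right, because no administrative censoring can occur before month 24 and both medians lie below that.

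**The case against.** Several points on the other side carry weight.

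- **Counting ongoing subjects as ended.** A reader might infer that the plan treats subjects still in benefit as if benefit had stopped. The text does not say so; it is silent on how they are handled. The criticism survives because leaving them out also lowers the mean, and by more in each scenario above.
- **Meaning of descriptive statistics.** A reader might take the section to define the term as mean, SD and range. The list is open-ended and belongs to a general sentence about all demographic and analytic data, so it is the likely default and not a definition for this endpoint. Even so, the adjacent sentences contrast this duration with the variables sent to Kaplan-Meier, and nothing elsewhere reverses that.
- **Size.** A reader might infer a large bias as a matter of course. The documents give no rate of leaving without progression. With administrative censoring only, the error in the mean is 3 to 12% at the documented medians, and the median of observed times is right. Those medians describe PFS in all subjects; duration among those with benefit may be longer, which would raise the error, but the documents do not say by how much.
- **Redundancy.** PFS and duration of response already go to Kaplan-Meier, and a swimmer plot is allowed, so a reader would not judge durability from this summary alone. This lowers the stakes. It does not give the stability half of the objective a valid summary.
- **The duration-of-response sentence.** Read literally, "For all other subjects, duration of objective response will be censored at the day of the last tumor assessment" follows a clause about responders and so appears to censor non-responders and leave ongoing responders with no rule. Non-responders have no start date for this variable, and the parallel PFS sentence makes the intent clear. This is a wording repair and not a second statistical fault.

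**Conclusion.** The concern holds as a should-fix point. Section 8.2.3 names an unsuitable method for a right-censored secondary endpoint and gives that endpoint no start, end or censoring rule, so more than a detail is missing. A simple mean understates the duration under either handling of ongoing subjects. With ongoing subjects counted at their observed time, the shortfall runs from about 3% (7.4-month median) and 12% (12.9-month median) with administrative censoring only, to about 31 to 34% if a further 30% leave without progression.

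These sizes rest on exponential durations, uniform accrual, non-informative censoring and an assumed 0 to 30% of early leaving. A reader might go further and infer that the trial's efficacy conclusion is at risk. The documents do not support that: no hypothesis test, threshold or decision uses this duration, and the primary ORR test, the Simon rule and the sample size do not change.

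**What to change.** In Section 8.2.3:

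1. Define duration of clinical benefit in subjects with best response CR, PR or SD, from Cycle 1 Day 1 to progression or death, censored at the last tumor assessment.
2. Add it to the list of endpoints analysed by Kaplan-Meier, and report the median and landmark rates with confidence intervals.
3. Keep descriptive statistics for the clinical benefit rate only.
4. As a wording repair, open the duration-of-response censoring sentence with *For responders without documented progression or death*.

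The cost is a few sentences of text. The tumor assessments are already scheduled and the method is already in the plan, so no new data, visits or subjects are needed.
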